5.5 PROTOCOL DEVIATIONS

Major protocol deviations of interest may include, but are not limited to the criteria in Table 2.

Table 2. Criteria for Assessing Major Protocol Deviations

Number	Major Protocol Deviation
1	Violation of key* inclusion or exclusion criteria which may affect the assessment of the efficacy of the study drug

Number	Major Protocol Deviation
2	Administration of ESA for more than 4 weeks before Week 16; any duration from Week 16 to Week 24
3	Study drug compliance < 75% or >125% (up to Week 24)
4	Administration of prohibited concomitant medication that may impact evaluation of efficacy of the study drug*
5	Significant noncompliance with study procedures that may impact evaluation of efficacy of the study drug will be evaluated case by case*

*Subject to Medical Monitor's decision

The number and percentage of major protocol deviations will be categorized and summarized as deemed appropriate.

6 SUBJECT ACCOUNTABILITY AND DISPOSITION

The following subject data will be summarized and presented if applicable, by number and percentage:

- Subjects enrolled at each center, and for all centers combined (using the enrolled population)
- Subjects in each analysis set (using the enrolled population)
- Subjects who prematurely discontinued during the treatment period, and by discontinuation reason for the enrolled population.
- Subjects who complete the treatment period (will be considered as “completers”)
- Subjects who participated in the Post-treatment Follow-Up
- Subjects who completed the EOS Visit
- Subjects who entered extension study

Kaplan-Meier plots will be generated for premature treatment discontinuations showing one curve.

7 DEMOGRAPHICS AND OTHER BASELINE CHARACTERISTICS

7.1 DEMOGRAPHICS AND BASELINE CHARACTERISTICS

Demographic parameters and important baseline and disease characteristics will be summarized for the safety and FAS populations. These include but may not be limited to age, age group (18 to <65, 65 to <75, ≥75), sex, ethnicity, race, weight, body-mass index (BMI), Hb, baseline Hb categories (<10, ≥10 g/dL), iron repletion status at baseline, ferritin, ferritin group (<100, 100-<400, ≥400 ng/mL), TSAT and TSAT group (<20%, 20%-<40%, ≥40%), hepcidin, serum iron, iron deplete (ferritin <100 or TSAT <20%) vs. not, cardiovascular or cerebrovascular or thromboembolic medical history (yes vs. no), blood pressure (systolic ≥140 or diastolic ≥90 vs systolic <140 and diastolic <90), incident dialysis vs stable dialysis, starting dose, baseline ESA type, baseline ESA dose categories (low/medium/high/very high), vascular access at baseline.

Table 3. Baseline ESA Dose Categories

Baseline ESA dose categories	Epoetin (IU/Week)	Darbepoetin Alfa (ug/Week)	Mircera (ug/month)
Low	0 - < 5000	0 - < 25	0 - < 80
Medium	5000 - < 8000	25 - 40	80 – 120

High	8000 – 16000	> 40- 80	> 120- 200
Very High	> 16000	>80	>200

Identify dialysis based on medical history of interest CRF MHINTERM ((Dialysis (Peritoneal), Dialysis (Home Hemodialysis), and Dialysis (Hemodialysis). Dialysis start date equals to MHSTDAT if not partial. If it is partial and day is missing impute the date with 1st day of the month. If missing month and day, impute to January 1st.

ESA naive is defined as patients who started ESA for < 6 weeks prior to Day 1. ESA dependent is defined as patients who started ESA for \geq 6 weeks prior to Day 1.

ESA baseline window is defined as 28 days prior to enrollment and the date right before first dose. For patients with more than one ESA type at baseline, the ESA type that was administered immediately before Day 1 was used.

Total duration of ESA use is calculated from first chronic ESA use to date of first dose date.

Stable dialysis is defined as patients who have been on dialysis for $>$ 4 months at the time of enrollment into the study. Incident dialysis is defined as patients who have been on dialysis for \leq 4 months at the time of enrollment into the study.

Dialysis duration is calculated from first chronic dialysis date to date of enrollment.

In addition, 25%-75% values of Hb and platelets will be presented. Frequency distributions (number and percentage of subjects) will be presented for categorical variables.

The baseline characteristics, iron indices, and iron IV given between ESA naïve and those converted from ESA therapy will be summarized and presented in a table.

Descriptive statistics of baseline values for other parameters will be presented in their change from baseline tables.

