4. STUDY DESIGN

4.1. Description of the Study

[figure not shown]
This open-label single arm study is designed to evaluate roxadustat in maintaining Hb in ESRD subjects receiving in-center HD either after conversion from a stable ESA dose: ESA use ≥ 6 weeks prior to conversion to roxadustat dosing or as initial anemia treatment, in subjects with < 6 weeks of total ESA use prior to start of roxadustat dosing.

The study periods are:

- o Screening Period: Up to 6 weeks
- o Treatment Period: 24 weeks
- Post-Treatment Follow-Up Period: Subjects permanently discontinuing roxadustat, should have one final safety assessment (TEAEs and TESAEs) 28 days after the last roxadustat dose.

An extension of roxadustat treatment after 24 weeks may be offered to interested subjects within the context of this study protocol upon agreement of the study site until roxadustat is commercially available, or up to 1 year after completing the 24 weeks, whichever comes first.

Figure 2: Study Design Overview

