4.5. Starting Dose of Study Drug

4.5.1. Route of Administration: Oral (all tablets must be administered whole)

4.5.2. Dosing Frequency:

Subjects will be dosed three times weekly (TIW), except if a subject requires < 60 mg/week to maintain Hb levels, in which case dose frequency may be reduced in a stepwise fashion, e.g., to twice weekly (BIW), then once weekly (QW).

4.5.3. Initial Doses:

4.5.3.1. Conversion from ESA to Roxadustat:

The initial roxadustat dose is determined using a conversion table based on the subject's previous prescribed ESA dose in the last 4 weeks prior to enrollment (for Mircera[®]:in the last 8 weeks prior to enrollment) (Table 1).

Roxadustat treatment should start after the following intervals:

- Two days after stopping epoetin
- One week after stopping darbepoetin alfa
- Two weeks after stopping methoxy polyethylene glycol-epoetin beta (Mircera®)

If the converted initial dose exceeds the maximum dose of 3.0 mg/kg/dose then the next-lower dose step should be chosen as the initial dose.

Table 1: Conversion from ESA to Roxadustat

Previous dose of Darbepoetin alfa (mcg/week)	Previous Dose of Epoetin alfa (IU/week)	Previous Dose of Mircera® (mcg/month)	Starting Dose of Roxadustat (mg/dose TIW)
<25	< 5000	<80	70
25 to 40	5000 to 8000	80 to 120	100
>40	>8000	>120	150

4.5.3.2. Initiation of Roxadustat Dosing in subjects with < 6 weeks of prior ESA or no prior ESA use:

The initial roxadustat dosing is based on broad body weight categories (estimated dry weight at enrollment) as described in Table 2.

Table 2: Initial Roxadustat Dosing:

Body Weight Category	< 100 kg	≥ 100 kg
Roxadustat Dose (TIW)	70 mg	100 mg

Note: Weight in HD subjects = subject's estimated dry weight at enrollment.

4.5.3.3. Dose Adjustments:

Dose adjustment evaluations will be made every 4 weeks and doses will be titrated based on Hb level and rate of Hb change according to Appendix 1. Any potential dose escalation/dose reduction will be at pre-defined dose step increments.

A dose reduction may be implemented at any time if the following criteria are met:

- Rate of Hb rise > 2 g/dL within 4 weeks: reduce dose by 1 dose step
- Hb level \geq 13g/dL: hold dose, until Hb drops to < 12g/dL, resume dosing at 2 dose steps lower

Any dose adjustment will reset the dose-adjustment window to every 4 weeks thereafter (e.g., dose adjustment for a qualified reason at Week 6 leads to next dose adjustment at Week 10).

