5. STUDY ENROLLMENT AND WITHDRAWAL

5.1. Inclusion Criteria

A subject is eligible for the study if all of the following criteria are met:

- 1. Subject has been informed of the investigational nature of this study and has given written informed consent in accordance with institutional, local, and national guidelines
- 2. Subject is ≥ 18 years of age
- 3. Receiving in-center hemodialysis for end stage renal disease (ESRD)
- 4. Prior ESA use:
 - For a subject converting from an ESA: On ESA ≥6 weeks and the prescribed ESA dose remain stable (as determined by PI) during the 4 weeks prior to initiating roxadustat treatment
 - Subject is initiating anemia treatment: Defined as: < 6 weeks of prior ESA use or no prior ESA use.
- 5. Vascular access must be a functioning native arteriovenous fistula or graft with adequate flow in the opinion of the investigator, or permanent tunneled catheter.
- 6. Screening Hb (based on central lab value; measured within 10 days prior to initiating roxadustat treatment):
 - Subjects converting from an ESA: screening Hb is between 9.0 to 12.0 g/dL
 - Subjects initiating anemia treatment: screening Hb is < 10.0 g/dL
- 7. Ferritin ≥ 50 ng/mL, Transferrin saturation (TSAT) ≥ 10% at screening (subject may qualify after receiving iron supplement per local standard of care)
- 8. Subject's alanine aminotransferase (ALT) and aspartate aminotransferase (AST) are ≤ 3 x upper limit of normal (ULN), and total bilirubin (TBL) is ≤ 1.5 x ULN at screening and prior to initiating roxadustat treatment. TBL up to 2 x ULN may be allowed if AST and ALT are within normal limit)
- 9. Subject's body weight (estimated dry weight in HD subjects) is 45.0 to 160.0 kg

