4.2 EXPLORATORY ENDPOINTS

- Proportion of subjects with a mean Hb level within 10-12 g/dL from Week 16 to Week 24
- Proportion of subjects with Hb > 12 g/dL any time during treatment
- Proportion of subjects with Hb > 13 g/dL any time during treatment
- Percentage of time with Hb, values within 10.0 to 12.0 g/dL from Week 16 to Week 24
- Time to first RBC transfusion
- Proportion of subjects with a mean Hb level ≥ 10 g/dL in the first 8 weeks after conversion or initiation of treatment
- Proportion of subjects with a mean Hb level ≥ 10 g/dL (averaged from Week 16 to Week 24) based on baseline ESA use status ≥ 6 weeks (conversion from ESA to roxadustat based on prior ESA use) and < 6 weeks (initiation of roxadustat based on body weight)
- Evaluate the utilization of IV iron (IV iron use/4 weeks)

- Evaluate the effect on iron indices
- Evaluate dosing adherence
- Conversion subjects: Comparison of starting dose of roxadustat to roxadustat dose at Weeks 16 to 24
- Mean number of dose adjustments (including dose-hold) during study
- Proportion of subjects requiring blood/pRBC transfusion from Week 5 (Day 29) to Week 24/ET.
- Proportion of subjects requiring rescue therapy (blood/pRBC transfusion or ESA rescue) from Week 5 (Day 29) to Week 24/ET

In addition to the exploratory endpoints in the protocol, additional exploratory efficacy endpoints of interest are presented in this section.

RBC transfusion data is collected in the Blood Transfusions form of the eCRF.

For efficacy evaluation, Hb values will be censored for 4 weeks if blood/pRBC is administered during the treatment period. Hb results obtained from the central laboratory will be used to determine the Hb response.

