13.2.7 Missing Date Information for Prior or Concomitant Medications

For prior or concomitant medications, including rescue medications, incomplete (i.e., partial missing) start date and/or stop date will be imputed. When the start date and the stop date are both incomplete for a patient, impute the start date first.

- **Incomplete Start Date**

The following rules will be applied to impute the missing numerical fields. If the stop date is complete and the imputed start date is after the stop date, then the start date will be imputed using the stop date.

Missing day and month

If the year of the incomplete start date is the same as the year of the first dose date of study medication, then the day and month of the first dose date will be assigned to the missing fields.

If the year of the incomplete start date is not the same as the year of the first dose date of study medication, then January 1 will be assigned to the missing fields.

Missing month only

Treat day as missing and replace both month and day according to the above procedure.

Missing day only

If the month and year of the incomplete start date are the same as the month and year of the first dose date of study medication, then the day of the first dose date will be assigned to the missing day.

If the month and year of the incomplete start date are the same as the first dose date of study medication, then the first day of the month will be assigned to the missing day.

- **Incomplete Stop Date**

The following rules will be applied to impute the missing numerical fields, if needed. If the last dose date of study medication is missing, impute it with the last visit date. If the imputed stop date is before the start date (imputed or non-imputed start date), then the imputed stop date will be equal to the start date.

Missing day and month

If the year of the incomplete stop date is the same as the year of the last dose date of study medication, then the day and month of the last dose date will be assigned to the missing fields.

If the year of the incomplete stop date is not the same as the year of the last dose date of study medication, then December 31 will be assigned to the missing fields.

Missing month only

Treat day as missing and replace both month and day according to the above procedure.

Missing day only

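### The SAP does not say which definition of ESA cohort governs, and its time-since-start rule and partial-date rule can label subjects differently from the cohort in which they were enrolled and dosed (minor)

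*SAP*

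**What the plan says.** Three descriptions of the two ESA cohorts are in force.

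- **Amount of use.** Inclusion criterion 4 in Protocol 5.1 puts a subject in the initiation cohort with "< 6 weeks of prior ESA use or no prior ESA use". Protocol 4.1 describes the same cohort as initial treatment "in subjects with < 6 weeks of total ESA use prior to start of roxadustat dosing".
- **Time since start.** SAP 7.1 states that "ESA naive is defined as patients who started ESA for < 6 weeks prior to Day 1", and defines ESA dependent as the complement at six weeks or more. The same section adds that "Total duration of ESA use is calculated from first chronic ESA use to date of first dose date".
- **Dosing route.** SAP 4.2, repeated in 9.2.2, splits the exploratory Hb ≥ 10 g/dL endpoint into conversion dosed from prior ESA and "< 6 weeks (initiation of roxadustat based on body weight". This matches Protocol 4.5.3.2 for initiation subjects: "The initial roxadustat dosing is based on broad body weight categories (estimated dry weight at enrollment".

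For partial dates, SAP 7.1 gives a specific rule for the start of dialysis but none for the start of ESA. SAP 13.2.7 covers prior and concomitant medications in general. When day and month are missing and the year is that of first dose, "then the day and month of the first dose date will be assigned to the missing fields". A year-only date from another year goes to January 1. If a complete stop date falls before the imputed start, the start is reset to the stop date. The second branch for a missing day reads "are the same as the first dose date of study medication, then the first day of the month will be assigned", which repeats the condition of the first branch.

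**The concern.** Amount of use and time since start agree only for a subject whose ESA use ran without a break up to Day 1. Otherwise the SAP 7.1 label can differ from the cohort that set the subject's eligibility and dosing table. Partial start dates can add errors in either direction.

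The cohorts are not interchangeable. Protocol 5.1 requires a screening Hb of 9.0 to 12.0 g/dL for conversion and below 10.0 g/dL for initiation. A conversion subject labelled naive may therefore enter the initiation response rate with Hb already at or above the response threshold of 10 g/dL. The primary objective names both cohorts, so their separate rates will be read even though they are exploratory. With no stated precedence, two programmers could produce different tables from this plan.

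**Working it through.** The plan gives no figure on this point to reproduce. The check applies the written rules to dates, with 6 weeks = 42 days.

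**1. Complete dates.** The protocol counts days of use; SAP 7.1 counts days of use plus any ESA-free gap. The labels disagree when use < 42 and use + gap ≥ 42. The documents state gaps only for conversion subjects (Protocol 4.5.3.1: 2 days for epoetin, 7 for darbepoetin, 14 for Mircera), so applying them to an initiation subject is an assumption.

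| Assumed gap | Use giving disagreement |
|---|---|
| 2 days | 42 − 2 = 40, so 40–41 days |
| 7 days | 42 − 7 = 35, so 35–41 days |
| 14 days | 42 − 14 = 28, so 28–41 days |

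A short course months before Day 1 also disagrees, whatever its length below six weeks, if it is taken as the ESA start.

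**2. Partial dates, if 13.2.7 applies to pre-study ESA.**

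| Pattern | True start, first dose | True days | Imputed start | Imputed days | Effect |
|---|---|---|---|---|---|
| Year only, same year as first dose | 10 Jan 2021, 15 Jun 2021 | 156 | Day 1, or an earlier complete stop date | 0, or 2 to 14 at the stated intervals | Dependent becomes naive |
| Year only, earlier year | 28 Dec 2020, 20 Jan 2021 | 23 | 1 Jan 2020 | 385 | Naive becomes dependent |
| Day missing, other month (intended reading) | 25 Feb 2021, 20 Mar 2021 | 23 | 1 Feb 2021 | 47 | Naive becomes dependent |
| Day missing, same month | any | at most 30 | Day 1, first of month or stop date | at most 30 | None: always below 42 |

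**3. How often a year-only date would flip.** This needs an assumption: first-dose dates spread over one calendar year and true starts uniform over the preceding W days.

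- For a first dose k days after 1 January, k − 41 starts lie in the same year and at least 42 days back (k from 42 to 364). Their sum is 323 × 324 / 2 = 52,326.
- All starts at least 42 days back number 365 × (W − 41).
- W = 365: 52,326 / 118,260 = 44.2%. W = 730: 52,326 / 251,485 = 20.8%. W = 1,825: 52,326 / 651,160 = 8.0%.

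In the other direction, among true starts less than 42 days back (365 × 41 = 14,965), a year-only date flips 41 × 42 / 2 = 861, or 5.8%. A missing day in another month flips 5,373, or 35.9%. All of these are shares of subjects with that kind of partial date, not of all subjects. The documents do not say how many such dates there are.

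**4. The printed missing-day rule.** As written, a same-month date gets two answers and an other-month date gets none. The parallel adverse-event start rule (SAP 13.2.6) and the medication stop-date rule in 13.2.7 both carry the negation, so the intended wording is clear.

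**The case against.** The strongest reply is that SAP 7.1 belongs to demographics. The one efficacy endpoint split by cohort is described in SAP 4.2 and 9.2.2 by dosing route, which is close to the remedy proposed here. This stands as far as it goes: a reader might infer that the 7.1 label drives that endpoint, and the documents do not say so. They do not exclude it either. The SAP 7.1 baseline table sets ESA naive beside those converted, mixing the two vocabularies.

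A reader might also infer several stronger points that the documents do not support:

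- **That partial ESA starts are generally moved to Day 1.** Only two patterns go there, and one of them cannot change cohort. A complete stop date before Day 1 overrides the move, although the label comes out the same.
- **That 13.2.7 certainly governs pre-study ESA.** SAP 9.2.8 places rescue ESA on the concomitant medication form, but no form is named for pre-study ESA.
- **That never-users fall outside the analysis.** The 7.1 wording omits them, but SAP 3.1 covers any ESA treatment below six weeks, and the dosing text in SAP section 2 includes them expressly.
- **That time on ESA during screening creates a discrepancy.** Protocol 4.1 also counts use up to the start of roxadustat. Only ESA-free time differs.
- **That the double answer for same-month dates moves subjects.** Both answers lie within 30 days of Day 1.

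It is also fair that the disagreement from a short gap alone sits in narrow bands of use.

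**Conclusion.** The point holds, at minor severity. The SAP contains a time-since-start definition that departs from the protocol's amount-of-use definition and from its own dosing-route description, and it does not rank them. Mislabelling is possible with complete dates. If 13.2.7 is taken to cover pre-study ESA, it is possible in both directions with partial dates. The missing negation in 13.2.7 is a plain drafting error whatever is decided about cohorts.

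The reach is limited to the exploratory Hb ≥ 10 g/dL rate by ESA status and the baseline comparison in SAP 7.1. The starting-dose comparison that SAP 4.2 restricts to conversion subjects, also exploratory, would follow whichever definition is chosen. The main Hb endpoint pools the cohorts, no hypothesis is tested (SAP 11), and ESA cohort is not among the forest-plot subgroups in SAP 9.3.

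One misplaced subject moves the rate in a cohort of n by at most 1/n. The documents give neither n nor the number misplaced, so no overall size can be stated.

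**What to change.** In the SAP:

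1. State that the analysis cohort is the one in which the subject was enrolled and dosed, taken from inclusion criterion 4 and the dosing table used, with never-users in the initiation cohort. Starting dose alone will not do, because 70 mg and 100 mg appear in both tables. Mismatch with the enrolled cohort is then zero by construction.
2. Use ESA dates only to describe duration of prior use. The date-derived status can be shown as a sensitivity analysis.
3. Exclude pre-study ESA from the rule that assigns the first-dose date, and give it its own partial-date rule, as SAP 7.1 already does for dialysis start.
4. Insert the missing negation in the second missing-day branch of 13.2.7.

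The cost is SAP wording, with no change to treatment or visits. The documents describe no dedicated cohort field, so the sponsor should confirm that the eligibility record identifies which limb of criterion 4 each subject met.

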2.6. Roxadustat Dose Rationale

The starting roxadustat doses and dose titration algorithm in this study are based on Phase 3 program involving ESRD patients with anemia who converted to roxadustat from stable ESA and patients who never used ESA before. These dosing schedules effectively corrected anemia and or maintained Hb levels close to 11.0 g/dL.

Analysis of the Hb time course after initiation of treatment with roxadustat in patients previously not on ESA treatment stratified by body weight indicated that the starting doses for patients not previously receiving ESA treatment should be 70 mg for patients with a body weight of <100 kg, and

Confidential Page 27 of 69

Protocol FGCL-4592-096 A01

Roxadustat 100 mg for patients with a body weight of ≥100kg. The proposed dose adjustment algorithm, applied

every 4 weeks, effectively maintained Hb levels close to 11.0 g/dL in these patients. For patients previously treated with an ESA, the applied starting doses of roxadustat (based on the

conversion table) in conjunction with the dose adjustment algorithm resulted in Hb levels that were maintained close to 11.0 g/dL. The full dose range of 20 to 400 mg TIW was utilized in the Phase 3 dialysis studies.

In this study, the initial dose of roxadustat will be determined by the subject's average prescribed ESA dose in the last 4 weeks prior to enrollment if on epoetin or darbepoetin (8 weeks if on Mircera®).

Using the conversion table (Table 1), in this study, subjects will receive starting roxadustat doses of 70 mg, 100 mg, 150 mg, or 200 mg. If the converted initial dose exceeds the maximum dose of 3.0 mg/kg/dose then the lower dose step should be chosen as the initial dose. Roxadustat doses will be administered at a frequency of TIW. If a subject requires < 20 mg TIW (i.e., < 60 mg per week) to maintain a Hb level of 11±1 g/dL, the dosing frequency should be reduced in a step-wise fashion e.g. TIW to BIW, BIW to QW, QW to Q-2 Week etc.

2.6.1. **Maximum Dose for Roxadustat**

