9.2.2 Hb Level

- Proportion of subjects with a mean Hb level ≥ 10 g/dL in the first 8 weeks after conversion or initiation of treatment
- Proportion of patient with a mean Hb level ≥ 10 g/dL (averaged from Week 16 to Week 24) based on baseline ESA use status ≥ 6 weeks (conversion from ESA to roxadustat based on prior ESA use) and < 6 weeks (initiation of roxadustat based on body weight)

For the Hb level exploratory analysis above, a MI method will be used. The imputation data will be generated in a method similar to the one described in [section 9.1.1](#). Similarly, the Rubin's method will then be used to combine the estimates of the proportion of responders and standard errors from each of the PROC FREQ procedure.

- Proportion of subjects with a mean Hb within 10-12 g/dL from Week 16 to Week 24
- Proportion of subjects with Hb > 12 g/dL any time during treatment
- Proportion of subjects with Hb > 13 g/dL any time during treatment
- Percentage of time with Hb values within 10.0 to 12.0 g/dL from Week 16 to Week 24

For the Hb level exploratory analysis above, observed Hb values will be used.

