9.3 SUBGROUP ANALYSIS

Primary efficacy endpoints will be presented by forest plots based on the following subgroups: sex, age group, baseline Hb categories, baseline iron status, cardiovascular/cerebrovascular/thromboembolic medical history, starting dose, participating dialysis organizations, and baseline ESA dose categories. Overall summary of TEAEs will be analyzed by subgroups of starting doses of roxadustat.

Other endpoints of interest may be analyzed by the subgroups listed above as needed.

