11 INTERIM ANALYSIS

An interim analysis may be performed to report topline results at the Sponsor's discretion. Since no statistical hypothesis testing is performed for this study, no multiplicity adjustment is required.

For better execution and understanding, certain data points (e.g., data linked to dose adjustments, iron supplementation, etc.) may be analyzed by patients participating under each dialysis organization (i.e., all patients, patients from DaVita, and patients from USRC), as needed.

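### SAP Table 3's baseline ESA-dose categories do not cleanly match the ESA conversion bands, and no planned analysis shows response by band among converters only

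*SAP*

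**What the plan says.** **Conversion subjects.** Protocol 4.5.3.1 (Table 1) sets the starting dose from three bands of prior ESA dose, and SAP section 2 (Table 1.1) repeats the table. Protocol 2.6 bases it on the "average prescribed ESA dose in the last 4 weeks prior to enrollment if on epoetin or darbepoetin (8 weeks if on Mircera"). Protocol 4.5.3.1 gives the Mircera period as "in the last 8 weeks prior to enrollment", and SAP section 2 carries the same rule.

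**Initiation subjects** (under 6 weeks of ESA, or none). ESA dose plays no part in their starting dose. Protocol 4.5.3.2: "The initial roxadustat dosing is based on broad body weight categories (estimated dry weight at enrollment").

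**Analysis categories.** SAP 7.1, Table 3 sorts baseline ESA dose into Low, Medium, High and Very High for each agent, with Low starting at 0. The period is set once for all agents: "ESA baseline window is defined as 28 days prior to enrollment and the date right before first dose". SAP 7.1 does not say how doses in that period become a weekly or monthly figure. It neither restricts the categories to conversion subjects nor provides a level for no ESA.

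**Use.** The subgroups for the forest plots in SAP 9.3 include "starting dose, participating dialysis organizations, and baseline ESA dose categories". SAP 9.2.2 separately reports the responder proportion by ESA-use status, namely at least 6 weeks ("conversion from ESA to roxadustat based on prior ESA use) and < 6 weeks (initiation of roxadustat based on body weight").

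**The concern.** The primary objective is to confirm the dosing regimens in converted and in ESA-naive subjects. For a converter, the regimen starts from a band of prior ESA dose. Of the planned displays, the forest plot by baseline ESA-dose category comes closest to showing how each band performed, and a reader will probably use it that way.

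That use requires two things: that the rows hold the subjects who fell in each band, and that they hold no one dosed by another rule. Neither is secured. The second matters because the two groups enter at different haemoglobin levels (Protocol 5.1): 9.0 to 12.0 g/dL for converters and below 10.0 g/dL for initiators. The plotted outcome is a mean haemoglobin of at least 10 g/dL. A row that mixes the groups may say as much about its mix as about the conversion band.

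**Working it through.** The plan gives no figure to reproduce here. The check sets the definitions side by side.

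**1. Cut-points.** Low is matched to the 70 mg band, Medium to 100 mg, and High or Very High to 150 mg.

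| Agent | Conversion table (70 / 100 / 150 mg) | SAP Table 3 (Low / Medium / High / Very High) | Differ at |
|---|---|---|---|
| Epoetin, IU/week | <5000 / 5000 to 8000 / >8000 | 0 to <5000 / 5000 to <8000 / 8000 to 16000 / >16000 | exactly 8000 |
| Darbepoetin, mcg/week | <25 / 25 to 40 / >40 | 0 to <25 / 25 to 40 / >40 to 80 / >80 | none |
| Mircera, mcg/month | <80 / 80 to 120 / >120 | 0 to <80 / 80 to 120 / >120 to 200 / >200 | none |

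A comparison over epoetin 0 to 30000 in steps of 1, darbepoetin 0 to 200 in steps of 0.1 and Mircera 0 to 400 in steps of 0.1 finds one mismatch, at epoetin 8000. At 7999 both place the subject in the middle, and at 8001 both place the subject above it. The conflict is also internal to the SAP (Table 1.1 against Table 3). With Medium as 5000 to 8000 and High as >8000 to 16000 there are no mismatches.

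**2. Mircera look-back.** The protocol value is taken as (month before last + last month) / 2, and the SAP value as the last 28 days alone. The histories are assumed, in mcg.

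| Month before last, last month | 8-week mean | Conversion band | 28-day category |
|---|---|---|---|
| 100, 100 | 100 | 80 to 120 | Medium (agrees) |
| 75, 100 | 87.5 | 80 to 120 | Medium (agrees) |
| 50, 100 | 75 | <80 | Medium |
| 75, 150 | 112.5 | 80 to 120 | High |
| 150, 100 | 125 | >120 | Medium |
| 250, none in window | 125 | >120 | Low |

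A subject can move only if the dose changed between the two months or, where administered doses are counted, if a dose falls outside the window. The entry criteria do not exclude the first case. Protocol 5.1 asks only that the "prescribed ESA dose remain stable (as determined by PI) during the 4 weeks prior to initiating roxadustat treatment", which leaves weeks 5 to 8 unconstrained.

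**3. Who enters the rows.** Initiators with some ESA use have an agent and a dose, and nothing in SAP 7.1 or 9.3 keeps them out. For zero-ESA subjects the documents are silent. A literal reading of the range from 0 puts them in Low; having no agent column, they might instead be left unclassified.

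If initiators make up a fraction w of a row, and converters and initiators respond at rates pC and pI, the row shows (1 − w)·pC + w·pI. It departs from the converters' own rate by w·(pC − pI). None of these values is in the documents. Assuming pC = 85% and pI = 65%, the departure is:

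- w = 0.10: 0.10 × 20 = 2 points
- w = 0.25: 0.25 × 20 = 5 points
- w = 0.50: 0.50 × 20 = 10 points (60 of each: (51 + 39)/120 = 75%)

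It is zero if the two groups respond alike.

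**4. Whether another planned analysis fills the gap.**

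- *Starting-dose subgroup (SAP 9.3).* Doses of 70 and 100 mg arise from both the conversion table and the body-weight table. The 3.0 mg/kg limit can also move a converter to a lower step: 150/3.0 = 50 kg, entry is allowed from 45 kg, and this is before the rounding allowance in Protocol Appendix 1. Starting dose therefore does not identify the band.
- *ESA-use status (SAP 9.2.2).* This separates converters from initiators but does not divide converters by band.
- *Starting dose against Weeks 16 to 24 dose (SAP 9.2.6).* This describes doses, not haemoglobin response.

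**The case against.** The strongest reply is that Table 3 was never declared a test of the conversion table. It is a baseline descriptor with four levels against the conversion table's three, and even perfect alignment would not reproduce assigned dose because of the mg/kg limit. Related questions are covered elsewhere: response by ESA-use status, starting dose as its own subgroup, and a split at baseline haemoglobin of 10 g/dL, which addresses part of the entry difference. Initiators will also have been titrated for 16 weeks before the evaluation window, so their lower entry level need not persist. Finally, the plan is descriptive: "Since no statistical hypothesis testing is performed for this study, no multiplicity adjustment is required".

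Much of this stands and limits the size of the point. What it does not supply is a display by conversion band among converters. Nor does it explain why one SAP table contradicts another at epoetin 8000, or why the Mircera period differs from the one that set the dose.

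A reader might go further and infer that the subgroup results say nothing about the conversion regimen. The documents do not support that: two agents have identical cut-points and the third differs at one value. A reader might also infer that all Mircera subjects are misplaced, but a subject on an unchanged dose, with doses inside the window, is classified correctly. And it cannot be said that zero-ESA subjects are in Low; the SAP leaves that open.

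**Conclusion.** The ESA-dose subgroup is misaligned with the conversion bands in three limited ways. Two are plain conflicts of text: the epoetin boundary at 8000 IU/week, and the Mircera period of 28 days against 8 weeks. The third is an omission: nothing limits the categories to conversion subjects, so initiators with under 6 weeks of ESA can appear in any row. As written, no specified analysis shows response by conversion band among converters only.

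The size is minor to moderate. One descriptive forest-plot subgroup and one baseline table are affected; the overall primary proportion, its confidence interval and N do not change. The documents do not give the number on exactly 8000 IU/week, the share on Mircera or the share of initiators. The Mircera effect depends on a dose change 4 to 8 weeks before enrolment, or on administered doses being used. The 2-to-10-point range for mixing rests on assumed response rates and an assumed share of initiators. Which starting dose suits any ESA dose is not judged here.

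**What to change.** In SAP 7.1 and 9.3:

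1. Define the baseline ESA-dose categories for conversion subjects only, and show initiation subjects, with or without some ESA, as a separate row.
2. Reconcile the Table 3 epoetin boundary with SAP Table 1.1: Medium 5000 to 8000 and High >8000 to 16000, as analysis categories only.
3. Classify by average prescribed ESA dose over the protocol's look-back (4 weeks; 8 weeks for Mircera), and state the calculation. Alternatively, classify by the ESA dose actually used to assign the starting dose, which removes the window question altogether.

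The cost is SAP wording and derivation code. No new data are needed, provided the ESA history used to assign each starting dose was recorded. Sample size and the main analysis stay as they are.
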